7.4.3 Requirements related to reporting to Janssen Scientific Affairs, LLC

In addition to the above reporting, the SI will use the following guidelines in reporting adverse events and product quality complaints to Janssen Scientific, LLC.

Maintenance of Safety Information

All safety data will be maintained in a clinical database in a retrievable format. The Sponsor Investigator shall provide all adverse events, both serious and non-serious, in report format. However, in certain circumstances more frequent provision of safety data may be necessary, eg, to fulfill a regulatory request, and as such the data shall be made available within a reasonable timeframe at Janssen Scientific Affairs, LLC request.

Procedures for Reporting Safety Data and Product Quality Complaints (PQCs) for Janssen Medicinal Products to the COMPANY

All adverse events and special situations, whether serious or non-serious, related or not related, following exposure to a Janssen medicinal product are to be documented by the investigator and recorded in the CRF and in the subject's source records. Investigators will record in the CRF their opinion concerning the relationship of the adverse event to a Janssen medicinal product.

All (serious and non-serious) adverse events reported for a Janssen medicinal product should be followed-up in accordance with clinical practice.

SAEs and Special Reporting Situations

All serious adverse events that have not resolved by the end of the study, or that have not resolved upon discontinuation of the subject's participation in the study, must be followed until any of the following occurs:

- The event resolves
- The event stabilizes
- The event returns to baseline, if a baseline value/status is available
- The event can be attributed to agents other than the study drug or to factors unrelated to study conduct
- It becomes unlikely that any additional information can be obtained (subject or health care practitioner refusal to provide additional information, lost to follow-up after demonstration of due diligence with follow-up efforts)

The Sponsor Investigator will transmit all SAEs and special situations following exposure to a Janssen product under study in a form provided by Janssen Scientific Affairs, LLC in accordance with Section Transmission Methods, in English within 24-hours of becoming aware of the event(s).

All follow-up information for serious adverse events that are not resolved at the end of the study or by the time of subject withdrawal must be reported directly by the Sponsor Investigator, within 24 hours becoming aware, to Janssen Scientific Affairs, LLC using the Janssen Scientific Affairs, LLC Serious Adverse Event Report .

All available clinical information relevant to the evaluation of a related SAE, serious ADR or special situation is required.

The Sponsor Investigator is responsible for ensuring that these cases are complete and if not are promptly followed-up. A safety report is not considered complete until all clinical details needed to interpret the case are received. Reporting of follow-up information should follow the same timeline as initial reports.

Non-Serious AEs

All non-serious adverse events should be reported to Janssen Scientific Affairs, LLC according to the timeframe outlined in the Research Funding Agreement section entitled Reporting of Data.

PQC Reporting

A PQC may have an impact on the safety and efficacy of the product. Timely, accurate, and complete reporting and analysis of PQC information from studies are crucial for the protection of subjects, investigators, and Janssen Scientific Affairs, LLC, and are mandated by regulatory agencies worldwide. Janssen Scientific Affairs, LLC has established procedures in conformity with regulatory requirements worldwide to ensure appropriate reporting of PQC information. Lot and/or Batch no. s shall be collected or any reports failure of expected pharmacological action (ie, lack of effect). The product should be quarantined immediately and if possible, take a picture.

All initial PQCs involving a Janssen medicinal product under study must be reported to Janssen Scientific Affairs, LLC by the Sponsor Investigator within 24 hours after being made aware of the event. The Janssen contact will provide additional information/form to be completed.

If the defect for a Janssen medicinal product under study is combined with either a serious adverse event or non-serious adverse event, the Sponsor Investigator must report the PQC to Janssen Scientific Affairs, LLC according to the serious adverse event reporting timelines. A

sample of the suspected product should be maintained for further investigation if requested by Janssen Scientific Affairs, LLC.

Reporting Procedures for Reporting Safety Data and Product Quality Complaints (PQCs) for Non-Janssen Medicinal Products

For SAEs, special reporting situations and PQCs following exposure to a non-Janssen medicinal product under study, the Sponsor Investigator should notify the appropriate regulatory/competent authority or the manufacturer of that medicinal product (in the absence of appropriate local legislation) as soon as possible.

Transmission Methods

The following methods are acceptable for transmission of safety information to Janssen Scientific Affairs, LLC:

- Electronically via Janssen SECURE Email service (preferred)
- For business continuity purposes, if SECURE Email is non-functional:
- Facsimile (fax), receipt of which is evidenced in a successful fax transmission report
- Telephone (if fax is non-functional).

Please use the contact information and process information provided by Janssen Scientific Affairs, LLC

8. CORRELATIVE/SPECIAL STUDIES

8.1 Blood and tissue acquisition

Research blood draws will be processed within the laboratory of [name] at Stanford University and stored as cryopreserved peripheral blood mononuclear cells (green top tubes) and plasma (purple top tubes).

Excisional lymph node biopsy prior to first dosing, which will be processed and stored as single cell suspensions within the laboratory of [name] at Stanford University.

FNA biopsies will be processed within the laboratory of [name] at Stanford University and stored as single cell suspensions.

Leukapheresis to obtain peripheral blood mononuclear cells (PBMC) may be performed during the screening period (prior to Day 1) and at Day 37, if excisional biopsy is obtained at screening.

8.2 Storage of blood and tissue samples

Samples will be stored as viable single cells suspensions in liquid nitrogen and cell-depleted serum at -80°C within the laboratory of [name] at Stanford University. Remaining unused samples will be stored for potential future correlative studies including flow cytometric studies with additional potential biomarkers, gene expression analysis, and high-throughput sequencing of immunoglobulin and T-cell receptors.

Access to samples will be limited only to research personnel involved in performing the correlative studies. Samples will be labeled with a unique subject identification code and all sample consent, acquisition, handling, storage and processing will be in accordance with

HIPAA and any other state or federal laws or regulations concerning the use or storage of human tissue for research purposes.

8.3 Lymphocyte activity against autologous tumor (performed if adequate tumor sample):

PBL and/or PBMCs will be obtained from all subjects, as described above, cryopreserved, and thawed, then used to for detection of tumor-specific T-cell responses by flow cytometry.

Autologous tumors undergo negative selection with antibody-bound paramagnetic beads and are then activated for 72 hours with CpG. These activated tumor B-cells are irradiated to 50 Gy in a Cesium-137 irradiator then used as stimulator cells in 24 hour co-culture with autologous subject PBMCs collected at the specified time points. Negative controls run in parallel include PBMC incubated with media alone. Positive controls for lymphocyte functional capacity will include anti-CD3 plus anti-CD28 stimulation. After co-culture, PBMC are stained for CD4; CD8; and a panel of T cell activation associated markers. Tumor-specific immune responses are calculated as the increase in percentage of activated T-cell subsets (CD4 or CD8) specifically in response to co-culture with autologous tumor at post-treatment time points compared to pre-treatment time points.

8.4 Immunophenotyping of treated and untreated tumor sites

Cells recovered from fine needle aspiration of treated and any easily accessible untreated sites will be processed for analysis by flow cytometry. Multiparameter flow will be performed at the various time points to define immune populations including CD4 and CD8 T-cells, regulatory T-cells, follicular helper T-cells, B-cells (including the malignant B-cells), natural killer cells, dendritic cells and macrophages. The extent of immunophenotyping will depend on the availability of cells from each biopsy.

8.5 Anti-tumor antibody response (performed if adequate tumor sample):

For IgM expressing lymphomas, pre – and post – treatment serum will be incubated with autologous tumor cells, followed by staining with FITC-labeled anti-human IgG antibodies and detection by flow cytometry. Additionally, Western blotting of tumor cell lysate using sera followed by anti-human IgG detectors may be performed and anti-idiotypic humoral responses may be assayed.

Protocol Intratumoral Injection of SD-101, an Immunostimulatory CpG, in combination with Ibrutinib and Local Radiation in Relapsed or Refractory Low-Grade Follicular Lymphoma

9. STUDY CALENDAR

Procedures	Screen	Day 1 Week 1 RT	Day 2 Week 1 RT IT SD-101	Day 4 Week 1 FNA (optional)	Day 9 Week 2 FNA IT SD-101 Ibrutinib	Day 16 Week 3 IT SD-101	Day 23 and 30 Week 4 and 5 IT SD-101	Day 37 Week 6 Safety Assessment	Weeks 12, 24, 36, 48, 60, 72, 84 Safety and Response Evaluation	Final Study Visit
Visit Windows				+/- 1 day	+/- 2 days	+/- 2 days	+/- 2 days	+/- 7 days	+/- 10 days	
Written Informed Consent	X									
Inclusion/Exclusion Criteria	X									
History and Physical Exam	X								X	X
Adverse Event Evaluation			X		X	X	X	X		X
Concomitant Medication	X		X		X	X	X	X		X
Vital Signs and Performance Status	X		X		X	X	X	X		X
Urine Pregnancy Test	X ¹									
Tumor Biopsy ² (optional)	X ²									
Fine needle aspiration	X ³		X ³	X ³				X ³		X ³
Research Blood Samples ⁴	X				X		X ⁵	X	X	X
CBC with differential	X				X		X ⁶	X	X	X
Comprehensive Metabolic Panel	X				X		X ⁶	X	X	X
HIV and hepatitis testing	X ⁷									
LDH	X								X	X
Radiation		X(2 Gy)	X(2 Gy)							
SD-101 Injection			X ⁸	X ⁸	X ⁸	X ⁸				
Ibrutinib supply dispensed					X			X ⁹	X ⁹	
Imaging Studies (CT)	X								X ¹⁴	X ¹⁰
Bone Marrow Biopsy ¹¹ (conditional)									X ¹¹ (optional)	X ¹¹ (optional)
Apheresis ¹² (conditional)	X ¹²							X ¹²		
Additional Research Peripheral Blood ¹³ (conditional)	X ¹³				X ¹³	X ¹³		X ¹³	X ¹³	X ¹³

- ¹ Pregnancy test - for women of childbearing potential only
- ² Tumor excisional biopsy (optional) to be done during screening if indicated to rule out transformation. Tissue not needed for clinical diagnostics may be collected for use in correlative studies
- ³ Fine needle aspiration of the tumor site chosen for treatment at screening, Day 9 (prior to second SD-101 injection) and Day 37. Optional FNA on Day 4. Fine needle aspiration of additional tumor (outside of the radiation field) to be done concurrently if amenable to biopsy.
- ⁴ Consisting of 1 purple top tube.
- ⁵ The indicated research labs are collected on Day 23 and not Day 30
- ⁶ CBCD and CMP monitoring to be done at Day 23 and not Day 30
- ⁷ Hepatitis and HIV testing to include hepatitis B surface antigen, anti-HBc antibody, anti-HCV antibody, and anti-HIV antibody
- ⁸ Subjects must be monitored at least 30 minutes after all injections of SD-101 before discharge
- ⁹ Ibrutinib to be self-administered by subject starting on Day 10 and continuing daily until Week 96, disease progression, or removal from study. Event indicates dispensing of supply.
- ¹⁰ Imaging performed at final study visit only if there has not been interval imaging within the last 4 weeks
- ¹¹ Bone marrow biopsy (conditional) only if subject achieves a complete response by imaging to confirm complete response
- ¹² Apheresis (conditional) only if subject had excisional biopsy prior to treatment with sufficient sample to perform immune assay correlative study or, optionally, if patient has circulating lymphoma cells.
- ¹³ 7 green top tubes to be collected: This collection will occur for all patients at Day 9, Day 16, Week 12, and final study visit. Additionally, 7 green top tubes (conditional) will be collected for patients not undergoing apheresis at the following timepoints: screening and Day 37.
- ¹⁴ CT scans to be performed on Weeks 12; 24; 48; 72

10. MEASUREMENTS

10.1 Phase 1B - Primary Outcome Measure

The primary outcome measure for the phase 1b portion will be the observation of **dose-limiting toxicity**. This outcome measure assesses a safety issue. The outcome will be measured at each visit during the trial.

10.1.1 Dose-Limiting Toxicity Definition

DLTs are defined as:

Days 1-30:

- Any Grade 4 treatment-related toxicity;
- Any Grade ≥ 3 treatment related toxicity persisting despite adequate/maximal medical therapy and/or prophylaxis. [NOTE: Grade 3 or lower treatment related skin rash not requiring systemic steroid therapy or other immunosuppressive therapy or Severe (Grade 3) flu-like symptoms are not considered DLTs. Grade 3 rash may be treated by withholding ibrutinib and/or systemic corticosteroids for up to 7 days. If rash resolves or improves to Grade 1, subjects may be restarted at the same dose of ibrutinib. If Grade 3 rash recurs upon restarting ibrutinib, then this will be considered a DLT];
- Any Grade ≥ 3 non-hematologic study drug-related toxicity will be considered a dose-limiting toxicity
- Any Grade ≥ 3 hematological study drug-related toxicity
- Grade ≥ 3 treatment related clinical autoimmune reaction involving major organs, which are defined as liver, pancreas, lung, heart, kidney, bowel, bone marrow and CNS (including the eye) which does not resolve to baseline or Grade 1 within 6 weeks;
- Grade ≥ 3 Injection Site Reaction;

Days 31-731:

- Any Grade 4 treatment related non-hematologic toxicity;
- Any Grade ≥ 3 treatment related toxicity persisting despite adequate/maximal medical therapy and/or prophylaxis. [NOTE: Grade 3 or lower treatment related skin rash not requiring systemic steroid therapy or other immunosuppressive therapy or Severe (Grade 3) flu-like symptoms are not considered DLTs];
- Grade ≥ 3 treatment related clinical autoimmune reaction involving major organs, which are defined as liver, pancreas, lung, heart, kidney, bowel, bone marrow and CNS (including the eye) which does not resolve to baseline or Grade 1 within 6 weeks
- Any Grade ≥ 3 hematologic toxicity that persists despite protocol-defined dose-modification of ibrutinib. (see Section 4.1)

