4. TREATMENT PLAN

4.1 Dose de-escalation Study Design

The study will use a 6+3 design with a goal of determining the recommended phase 2 dose. We will enroll a cohort of 6 subjects, with a 3 mg dose of intratumoral SD-101 and 560 mg dose of oral ibrutinib. The proposed initial dose of SD-101 is below the maximum tolerated dose as determined in previous trials, and there is extensive data regarding the safety of treatment with ibrutinib at the FDA-approved dose of 560 mg. Because no additional toxicity is anticipated with combination therapy of SD-101 and ibrutinib, the 6+3 dose de-escalation design will be employed, permitting rapid confirmation of the safety of the combination therapy and selection of the recommended phase 2 dose while still allowing detection of any unanticipated toxicity.

If 0 or 1 subjects out of the initial 6 subjects experience a DLT, we will chose this dosing as the recommended phase 2 dose level. If 2 out of 6 subjects experience a DLT, we will expand the

cohort and enroll an additional 3 subjects at the same dose level. If 3 out of 6-9 subjects in the initial dose cohort experience a DLT, then the dose de-escalation cohort -1 will accrue. This dose de-escalation cohort will be treated with 1 mg intratumoral SD-101 and 560 mg ibrutinib. If \leq 2 out of 6 subjects in the dose de-escalation cohort experience a DLT, then this dose will be considered the RP2D. If 3 or more subjects in the de-escalation cohort experience a DLT, the study will be stopped.

Table 1. Dose Escalation Plan

Cohort	Dose (mg)	Total Enrollment per Cohort	Dose Escalation Rules
-1	1 mg SD-101 560 mg ibrutinib	6	1 of 6 or 2 of 6 DLT, RP2D is established 3 of 6 DLT, trial is stopped
1	3 mg SD-101 560 mg ibrutinib	6-9	0 of 6 or 1 of 6 DLT, RP2D is established at this level 2 of 6 DLT, expand cohort to 9 subjects 2 of 9 DLT, RP2D is established at this level 3 of 6-9 DLT, decrease to dose level -1
Phase 2 Expansion	RP2D	15	If the incidence of study drug-related DLTs as defined previously equals or exceeds 33% of treated subjects at RP2D dose level 1, enrollment will be stopped for dose level 1, and enrollment of 15 subjects will begin at dose level -1. If the incidence of study drug-related DLTs equals or exceeds 33% of treated subjects at RP2D dose level -1, then the trial is stopped

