4.3.6 Day 23 (+/- 2 days); Day 30 (+/- 2 days)

- Obtain vital signs/ ECOG performance status
- Assessment of adverse events and toxicity grading according the CTCAE v4.0
- Monitoring of concomitant medications
- CBC with Differential and platelet count at Day 23 visit
- Comprehensive Metabolic panel at Day 23 visit
- Administration of SD-101 intratumoral injection no. 4 (Day 23), no. 5 (Day 30) at the same injection site as previously
- Collection of 1 purple top tube for research correlates (Day 23 visit only)

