6. DOSE MODIFICATIONS

6.1 Dose/ Schedule Modifications of SD-101

The SD-101 dose of will not be reduced except by the rules listed in the study design. In the case of adverse events affecting the feasibility or safety of injection, as judged by the investigator, injections may be delayed or omitted until resolution of the adverse event to Grade ≤ 1 or baseline and after re-assessment by investigator. When doses are delayed, all five intratumoral injections may still be delivered, provided all five are given within a span of 8 weeks and there is a minimum interval of 3 days between injections. In the case of local injection site reactions that cause dose delays or modifications and are not DLTs, the Investigators are asked to avoid administering subsequent injections near to this site and to document the reaction with a photograph when possible.

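### A Grade 3 injection site reaction counts as a DLT on occurrence only to Day 30, the day SD-101 injection 5 is due, so a later reaction that does not persist is left out of the phase 1b 6+3 decision

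*Combined protocol and SAP*

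**What the plan says.** Section 10.1.1 defines DLTs in two lists. For Days 1-30 it includes "Grade ≥ 3 Injection Site Reaction" and, separately, any drug-related non-hematologic toxicity of Grade 3 or more. Both count as soon as they occur.

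The Days 31-731 list has no injection-site item. Its four criteria are:

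- "Any Grade 4 treatment related non-hematologic toxicity";
- treatment-related toxicity of Grade 3 or more that persists despite adequate or maximal therapy;
- a Grade 3 or higher autoimmune reaction in a major organ that has not resolved within 6 weeks;
- Grade 3 or higher "hematologic toxicity that persists despite protocol-defined dose-modification of ibrutinib. (see Section 4.1").

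Section 4.3 schedules SD-101 on Days 2, 9, 16, 23 and 30. Section 4.3.6 is headed "Day 23 (+/- 2 days); Day 30 (+/- 2 days") and assigns injection "no. 5 (Day 30) at the same injection site as previously". Section 6.1 allows delayed injections to be made up, "provided all five are given within a span of 8 weeks and there is a minimum interval of 3 days between injections". It also gives instructions for local reactions that hold up dosing without being DLTs: "In the case of local injection site reactions that cause dose delays or modifications and are not DLTs".

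Section 4.1 uses only the number of subjects with a DLT. With 0 or 1 of 6, 3 mg becomes the recommended phase 2 dose; with 2 of 6, three more subjects are added. "If 3 out of 6-9 subjects in the initial dose cohort experience a DLT", the next cohort receives 1 mg.

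**The concern.** SD-101 is the only drug whose dose the 6+3 rule can lower, and local reaction is a known effect of it. Section 5.1 reports one DLT in healthy volunteers, at 5 mg, which included local induration. The strict injection-site criterion should therefore cover every SD-101 injection.

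It does not. On schedule, injections 1 to 4 are each followed by about seven days under the on-occurrence rule. Injection 5 gets none to two, depending on where it falls in its window. A delayed injection may get none. If an uncounted reaction would have been the deciding DLT, the rule keeps 3 mg where it should have stepped down to 1 mg.

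Section 6.3 starts ibrutinib dose modification on Day 31, which explains why the hematologic criterion changes then. It gives no reason to drop a local reaction to SD-101.

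**Working it through.** **Dates.** Day 2 + 7k for k = 0 to 4 gives Days 2, 9, 16, 23 and 30, as in Section 4.3. The window for injection 5 is Days 28-32. Eight weeks from Day 2 is 2 + 56 = Day 58 (Day 57 if the first day is counted). Phase 1b has 6 to 9 subjects at 3 mg, so 30 to 45 injections, of which 6 to 9 are injection 5.

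**A Grade 3 injection site reaction against the two lists in Section 10.1.1.**

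| Reaction | Counted as a DLT? |
|---|---|
| Starts on or before Day 30 | Yes, on occurrence |
| Starts after Day 30, reaches Grade 4 | Yes, on occurrence |
| Starts after Day 30, Grade 3, persists despite therapy | Yes |
| Starts after Day 30, Grade 3, does not persist | No; it is neither a major-organ autoimmune reaction nor hematologic |

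The last row is the gap. Recording adverse events at the Day 37 visit (Section 4.3.7) captures such an event but does not make it a DLT.

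**A plausible risk per injection.** The documents give no Grade 3 rate for SD-101, so a range has to be assumed. Section 5.1 supplies indirect evidence from another CpG, with all reported adverse events Grade 1 or 2:

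- 18 mg study, 30 subjects: two stopped at 7 and 8 of 10 injections. If the other 28 had all 10, that is 28 x 10 + 7 + 8 = 295 injections.
- 6 mg study, 15 + 15 subjects: the schedule is two injections around radiation plus eight weekly, so 10. One subject stopped early and is left out; 29 x 10 = 290.

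The total is 585 injections with no Grade 3 reaction. The one-sided 95% upper bound is 1 - 0.05^(1/585) = 0.0051, about 0.5% per injection. The 18 mg study alone gives 1 - 0.05^(1/295) = 1.0%.

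**Effect on the 6+3 decision.** The plan states no operating characteristic for this rule, so there is no figure to reproduce. Let q be the risk per injection, equal and independent across injections, with no other DLTs. The risk per subject is p = 1 - (1 - q)^5 if all five injections count. It is p = 1 - (1 - q)^4 if injection 5 never counts, which is the worst case on schedule. Then

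P(de-escalate) = P(X6 >= 3) + P(X6 = 2) x [1 - (1 - p)^3], with X6 binomial (6, p).

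At q = 0.5% with all five counted, p = 0.02475 and the result is 0.00029 + 0.00831 x 0.0724 = 0.0009. With four counted, p = 0.01985 and the result is 0.00015 + 0.00546 x 0.0584 = 0.0005.

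| q | All five count | Injection 5 never counts |
|---|---|---|
| 0.5% | 0.09% | 0.05% |
| 1% | 0.6% | 0.3% |
| 2% | 3.8% | 2.2% |

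The 2% row lies above both bounds and is shown only for range. If half of the injection-5 reactions began by Day 30, the 1% row would read 0.6% against 0.5%. With a within-subject correlation of 0.2 it would be 0.24% against 0.16%.

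**Sensitivity to other DLTs.** A missed reaction is more likely to be decisive when other DLTs occur. Assume, without support in the documents, that 15% of subjects have another DLT, so p = 1 - 0.85(1 - q)^5 or 1 - 0.85(1 - q)^4. P(de-escalate) is then 15.6% against 14.7% at q = 0.5%, and 20.0% against 18.2% at q = 1%. The difference is 1 to 2 percentage points.

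**The case against.** The best defence is that the gap hardly matters. Section 5.1 reports intratumoral SD-101 with radiation, the same drug and route: no DLT in the completed 1, 2 and 4 mg cohorts of one trial, and no significant toxicity at 0.1, 1 and 3 mg in another. No denominators are given, so this yields no rate, but it points to few Grade 3 reactions. This stands, and it limits the size of the point.

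A second defence is the backstop. For the expansion, Section 4.1 stops enrolment at 3 mg and moves to 1 mg if the DLT incidence reaches 33% at any time in treatment, and it names Grade 3 injection site reaction in that count. A 3 mg dose with frequent late reactions would therefore probably be caught in phase 2. This also stands, but it does not correct the phase 1b count, and it suggests that such reactions were meant to count throughout.

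Third, the delay route may be rare. Section 6.1 requires recovery to Grade 1 or baseline and re-assessment before dosing resumes, and a Grade 3 reaction by Day 30 is already a DLT. Day 58 is a limit, not an expected date, and the frequency of delays cannot be derived.

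A reader might infer from the site's CpG experience, where local reactions usually cleared within two days, that the persistence criterion would seldom catch a late Grade 3 reaction. The documents do not support that. Those reactions were all Grade 1 or 2, and nothing is said about how long a Grade 3 reaction to SD-101 lasts.

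**Conclusion.** The definition in Section 10.1.1 is wrong as written, but the consequence is minor. A Grade 3 injection site reaction that starts after Day 30 and does not persist despite therapy is not counted in the phase 1b decision. On schedule this affects at most one of each subject's five injections, plus any that are delayed.

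Without other DLTs, the chance of de-escalating falls from about 0.09% to 0.05% at a risk of 0.5% per injection, and from 0.6% to 0.3% at 1%. These figures rest on near-complete courses in two studies of a different CpG, on equal and independent risks, and on losing every reaction to injection 5. A background of other DLTs raises the difference to 1 or 2 percentage points.

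Two stronger readings are not supported. One is that the rule is likely to select too high a dose: a visible effect from injection-site reactions alone needs a Grade 3 risk well above what Section 5.1 suggests. The other is that the relaxed hematologic criterion after Day 30 is a similar fault. That change coincides with the start of ibrutinib modification, and de-escalation lowers only SD-101.

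**What to change.** Add "Grade ≥ 3 Injection Site Reaction" to the Days 31-731 list in Section 10.1.1. In Section 4.1, state that the 6+3 decision is taken only after the last subject's reaction to the last SD-101 injection has been assessed, which on schedule is the Day 37 visit. The documents do not now say when the decision is taken.

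On schedule no visit is added, because Day 37 already collects adverse events. Its +/- 7 day window reaches Day 44, seven days after an injection on Day 37. A later last injection needs one extra contact about a week afterwards, at the latest about Day 58 + 7 = Day 65, since the calendar has nothing between Day 37 and Week 12. The price is a wait of about a week before the dose decision, longer if injections are delayed.

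I would not extend the strict rule to all Grade 3 non-hematologic toxicity attributed to SD-101. Ibrutinib is taken from Day 10, and attributing an event to SD-101 alone would be uncertain.

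As an editorial matter, the hematologic item's pointer to Section 4.1 should be to Section 6.3, where ibrutinib modification is described.
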